responses are across these studies, and how they are sustained for the entire study duration. In all three studies placebo decreases pain by at least 10% within 2-4 weeks and then by an additional 10-30% within 3 months. In **figure 3** (Cox2 NSAID study), placebo treatment decreased CBP pain by >50% in approximately 35% of the group. To unequivocally state that these are placebo responses, it is necessary to have a no-treatment, observation only, control group. Nonetheless, **figure 3** strongly suggests that the placebo effect may be dichotomous, hinting at the notion of two groups: responders and non-responders—this very notion is consistent with our preliminary results. Thus, *if we can identify chronic pain patients who will respond to placebo, then we can potentially decrease the pain in this group by about 30-50%, which would be highly clinically significant.*

Figures 2 and 3 also illustrate an important property of clinical placebo, namely a sustained relief from pain for many weeks. In contrast, experimental placebo studies, by design, only examine very short duration (hours to a few days) effects. Thus, brain circuitry identified for experimental placebo is unlikely to generalize to the clinically observed placebo effects. To our knowledge, using brain circuitry to predict the placebo response in the clinical setting has not been studied outside of our lab.

The current study design specifically addresses aspects of placebo trial design that have received ethical and scientific criticism. A recent review identifies 9 distinct potential sources of bias in placebo effect studies (Hrobjartsson et al., 2011). To circumvent these problems, we rely on randomized controlled trials (RCTs) and within-subject control washout periods, perform all procedures identically across all groups, all preliminary analyses are done blinded, un-blinding occurs only after the completion of data collection, and all primary outcomes are objective brain parameters. By controlling for these factors, the natural, biologically-based propensity for some subjects to be better placebo responders than others can be objectively identified based on the proposed clinical trials.

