4.0 TREATMENT PLAN AND STUDY INTERVENTION

4.1 Treatment Dosage and Administration

4.1.1 **Placebo Treatment:** Placebo capsules (gel caps filled with lactose NF), which will look identical to the active treatment capsules (see below), will be taken twice daily during treatment periods. During Phase 2, after a initial rating period and a 2-3 week washout of any of participant's current pain medications, participants will take placebo orally bid for 6 consecutive weeks (coming in every 3 weeks for follow-up visits and medication refills), followed by an additional 3 week washout period before study completion. One placebo

pill will be capsulated similarly to naproxen and the other will be encapsulated similarly to omeprazole.

The manufacturer for the placebo is Humco. The capsule shells (hard gelatin) will be manufactured by Capsugel (Coni Snap Size 00). Capsugel provides a certificate of analysis with each capsule batch ordered. Capsugel manufactures gelatin capsules from gelatin that complies with BSE requirements. Capsugel provides confidential detailed information about facilities, processes, articles used in manufacturing, processing, packaging, and storing of empty capsules through Type IV (Excipient) Drug Master Files submitted to the FDA. Inactive ingredients are cellulose and gelatin. Placebo capsules also contain FDC Blue #1 and FDC White.

- 4.1.2 **Active treatment:** 1 capsule of naproxen (500mg) and 1 capsule of omeprazole (20mg) will be taken orally twice daily based on the protocol for Phase 2 outlined in [3.1.1]. Each of these pills is encapsulated differently to avoid potential confusion when taking the medication. The active ingredient for the Naproxen tablets manufactured by Teva Pharmaceuticals or Amneal Pharmaceuticals, and the active ingredient for omeprazole is manufactured by Kremers. The capsule shells for both naproxen and omeprazole are manufactured by Capsugel and are the same material, size and color as those for the placebo (see 3.1.1. above).

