5.2 Procedures During Treatment

5.2.1 Schedule of Events for all participants

- Visit 1 (week-3): Consent, screening, and baseline pain/mood monitoring (45 min). Participants will complete the informed consent process and are evaluated for initial inclusion/exclusion criteria, and they will be asked to assess current back pain intensity on a VAS scale. They will be asked to assess current back pain intensity on a VAS scale (0-10mm, no pain to worst possible pain). A medical/pain history and physical examination including vitals will be completed. Blood will be drawn for an initial screen to obtain a complete blood count, chemistry panel, and liver function tests (data reviewed by [name]). Participants will be asked to discontinue their current pain medications ~14 days (2 weeks) prior to their first scanning visit. Participants will receive acetaminophen (rescue medication) at the time of the visit. They will be shown how to use the smart phone/computer application (and given a phone if necessary), and they will be instructed to rate their pain and mood with the app two times a day for the duration of the study. Participants will complete questionnaires and return within 2 weeks for the first MR imaging scans. This length of time is adequate to allow scheduling and permit flexibility for subjects' preferences, and to ensure that pain levels persist at or above 5/10 VAS collected from the pain rating app and that participants do not significantly respond (>20% decrease) to the acetaminophen rescue medication. In addition, the entry interview will be conducted at this visit.

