(2) The blinded assessor will be responsible for initiating the preprocessing of the brain images and extracting the connectivity values between frontal and sensorimotor regions ("sign permutation value"). This extraction will be done within 4 days after the MRI was collected, which provides enough time to calculate this connectivity and the likelihood of response (see below), as well as adequate time to give the result to the pharmacy (see below).

(3) After obtaining the connectivity values, the blinded assessor will enter these along with the 2 questionnaire subscores into the model on page 10 to determine subject group identification. The model generates a response likelihood from 0 to 1, and those individuals with a p-value \geq 0.5 will be labeled as responders; all others will be labeled as non-responders.

(4) After response group identification, the blinded assessor will then send an email with subject ID, classification group, and randomization code to the Northwestern University Research Pharmacy email [contact]. The research pharmacy will have two independent randomization sequences for responders (Group A) and non-responders (Group B). Each group independently will be allocated in a 3:3:1 ratio (active treatment, placebo treatment, and no treatment, respectively) by the research pharmacy. Therefore, the pharmacist will be unblinded to identification and treatment allocation.

The unblinded monitor who is responsible for phone app compliance will be partially unblinded, remaining blinded to active vs placebo assignments but unblinded with respect to treatment vs no treatment groups, as the pain rating app will query participants "Have you taken today's medication?" The remaining staff members will be completely blinded to both treatment vs no-treatment allocation and within the treatment allocation to active vs placebo treatments

A one-week interim period was chosen to allow enough time for selected study staff to run the prediction analysis and send this information to the pharmacy, as well provide another week of additional baseline pain app ratings. The duration of this period might be slightly longer or shorter depending upon how quickly the model is run, but it will be within the visit window specified in this protocol, which is \pm 5 days

- Visit 3 (week 0): Start of Treatment Period (30-45 min).

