Once classification has been made with regard to responder vs non-responder status participants will return for the next visit (V3). A set of questionnaires will be administered

and participants will be queried about changes to health experienced since the last visit. Vitals will also be collected. Participants who remain eligible will then be randomized to active treatment, placebo, or no treatment groups in a blinded fashion, which will be completed by the research pharmacy. The unblinded monitor will pick up study drug from the pharmacy prior to visit 3, if the participant is assigned to the treatment arm. Additionally, participants will receive only rescue medication in sufficient quantities until the next visit. The unblinded monitor will explain the medication regimen to the participant at that time. This is to ensure that the remaining study staff remain blind to treatment versus no-treatment group assignment. The placebo group, made up of predicted responders and non-responders, will receive two placebo capsules bid, and the active treatment group, also made up of predicted responders and non-responders, will receive one naproxen capsule (500mg) and one omeprazole capsule (20 mg) bid for the treatment period. Study medication will be dispensed in sufficient quantities until the next visit. The no treatment group and all participants in all groups will receive rescue medication by the research pharmacy in sufficient quantities to last them until the next visit. They will be asked to continue their daily pain/mood ratings, and to come back in 3 weeks for an interim visit, bringing back any remaining study medication at that time which will be accounted for by the research pharmacy.

Visit 4 (week 3): Continuing Assessment (30-45 min).

This visit will be completed entirely by the unblinded monitor; there is no clinical data being collected here – only safety data. All procedures will be performed as described for Visit 3. Adherence will be assessed by pill counting for those on treatment group, and participants will be queried about any side effects experienced. In addition one of the pictures for visit 2, 4, and 5 will be conducted (see section 13.III). Study medication and rescue medication will be dispensed in sufficient quantities until the next visit, as described in Visit 3. They will be asked to continue using the phone/computer app and to come back in 3 weeks for their end-of treatment (final) scan.

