- Visit 5 (week 6): End of Treatment/Start of Washout and Final Scan (60-90 min): Participants will undergo the same brain scanning session that they had on Visit 2, and all questionnaires, AE assessment, and treatment medication adherence procedures will be performed as they were in previous visits. Participants will be asked to stop the study medication (if applicable) and to start the washout period, and they will only be given rescue medication at this visit by the research staff (enough to last them until the last visit). In addition one of the pictures for visit 2, 4, and 5 will be conducted (see section 13.III). They will be asked to continue rating their pain and mood on the app and to return for the final visit in 3 weeks. Note that apart from the scanning session and administration of questionnaires via REDCap, all other aspects of this visit will be completed by the unblinded monitor to aid in the maintenance of the double-blind on the part of the study staff.
- Visit 6 (week 9): Final Visit/End of Washout (30-45 min): Any changes to health will be documented, and vitals will be collected. A short battery of questionnaires will be administered and participants will be compensated for all app ratings completed during the study.
- Interim periods: During weeks in between visits, participant data will be tracked with the assistance of a smart phone/computer application designed for the study (available through a secure website). Depending upon preference, we will download an app onto participants' phones or give them a link to use on their computers; in the case that a participant does not have a smart phone or easy access to a computer/internet, we will provide him/her with a smart phone that has the app already installed. Participants will be given a login and will be asked to use this application twice a day, morning and night for baseline and washout and right after they take their medication for treatment (if applicable). The app asks them to rate the severity of their pain and their mood on a Likert scale, and probes them as to

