6.0 RESPONSE CRITERIA

Treatment response is defined as a reduction in VAS pain intensity $>$ or equal to 20% from visit 1-visit 2 pain ratings, or by permutation testing for change in pain rating by 0.05 p-value. Such individuals are considered treatment "responders," whereas "non-responders" are defined as individuals who experience increased or stable pain levels throughout treatment periods, including reductions in pain $<$ 20% of baseline pain intensity.

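### App pain ratings are tied to capsule intake during treatment but to morning and night in baseline and washout, so the contrasts that define placebo response also contain a change in when pain is rated

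*Combined protocol and SAP*

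**What the plan says.** Section 5.2.1 (Interim periods) sets the app schedule: "twice a day, morning and night for baseline and washout and right after they take their medication for treatment (if applicable". Ratings stay at two a day throughout; what changes by period is the cue for making them.

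Other passages on the same procedure:

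- Section 5.2.1, Visit 1: participants are "instructed to rate their pain and mood with the app two times a day for the duration of the study". No clock times are given.
- Section 5.2.1, Visit 3, addressing all groups: "They will be asked to continue their daily pain/mood ratings". No rating time is given for the no-treatment arm.
- Section 4.1.1: capsules "will be taken twice daily during treatment periods", again without clock times.
- Section 5.2.1, between Visits 2 and 3: the monitor is unblinded to treatment versus no treatment "as the pain rating app will query participants" about that day's medication.
- Section 1.2: to limit bias, the investigators will "perform all procedures identically across all groups".

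The ratings carry weight. Section 8.2.1 lists them among the main pain outcomes, together with NRS and pain memory. Section 2.3.1 allows placebo response to be defined from them. Section 6.0 judges response by change "from visit 1-visit 2 pain ratings, or by permutation testing for change in pain rating by 0.05 p-value". Section 2.1.1 makes the no-treatment group the negative control for regression to the mean and other confounds.

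**The concern.** The change in rating cue falls exactly on the boundary across which response is measured, and it reverses at the boundary across which persistence is measured. A rise and fall in step with the capsules is also the pattern that the trial would read as a placebo effect.

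The no-treatment arm is there to remove what is not due to treatment, but it cannot remove a measurement change that it does not undergo. If pain differs by time of day, or between the moment after swallowing a capsule and other moments, that difference enters the capsule arms' change scores and responder labels.

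The written analysis does not deal with it. The longitudinal model in section 4.4 averages ratings by day and has no term for rating time, period or arm. Adjusting for clock time afterwards would help only in part, because a rating made just after a capsule occurs only in the capsule arms and only during treatment. That component is fully confounded with the effect being estimated.

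**Working it through.** **Schedule by arm and period (section 5.2.1)**

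| | Baseline | Treatment | Washout |
|---|---|---|---|
| Active | morning and night | after capsule intake | morning and night |
| Placebo | morning and night | after capsule intake | morning and night |
| No treatment | morning and night | not stated; capsule cue cannot apply | morning and night |

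Reading across a capsule-arm row, the cue changes twice. Reading down the treatment column, the capsule arms share a cue that the no-treatment arm cannot have. Active versus placebo is the one contrast with equal timing.

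**Illustration of size.** The plan states no figure to reproduce, so the shift and the within-person SD below are assumptions.

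Inputs:

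- Baseline ratings: 14 days (Visit 1 to Visit 2) × 2 a day × 75% compliance (Phase 1 average, section 1.2) = 21.
- Treatment ratings: 42 days × 2 × 75% = 63.
- Assumed: independent ratings, within-person SD 1.0 or 1.5, no true change, and a two-sided 0.05 test. The plan does not state sidedness; two-sided gives 2.5% in the direction of improvement.

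*Permutation rule*, normal approximation: z = shift / (SD × √(1/63 + 1/21)), where √(1/63 + 1/21) = 0.252. P(labelled improved) = 1 − Φ(1.96 − z).

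| Shift (points) | SD 1.0 | SD 1.5 |
|---|---|---|
| 0 | 2.5% | 2.5% |
| 0.1 | z = 0.40, 5.9% | z = 0.26, 4.5% |
| 0.3 | z = 1.19, 22% | z = 0.79, 12% |
| 0.5 | z = 1.98, 51% | z = 1.32, 26% |

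A simulated two-sided permutation test (2,000 runs, same counts) agrees. At a 0.5-point shift it flagged about 49% (SD 1.0) and 26% (SD 1.5), against 5% with no shift.

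*20% rule*, assuming a baseline of 6 (threshold 1.2 points) and mean true change 0: P = 1 − Φ((1.2 − shift) / SD of change). The SD of 3 is from section 8.1.2; 1.5 is assumed.

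| Shift (points) | SD 1.5 | SD 3 |
|---|---|---|
| 0 | 21% | 34% |
| 0.1 | 23% | 36% |
| 0.5 | 32% | 41% |

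*Group mean, one capsule arm versus no treatment*, t-test on change, SD 3, no true effect, nominal 5%:

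| Shift (points) | 90 vs 30 (section 5.3) | 60 vs 20 (section 8.1.1, gender supplement) |
|---|---|---|
| 0.25 | 6.8% | 6.2% |
| 0.5 | 12.3% | 9.8% |
| 1.0 | 34.8% | 24.7% |

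The within-person permutation rule is the most exposed, because many ratings per person make a small systematic shift significant.

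**The case against.** **The clock time may hardly move.** Ratings are twice a day and so are capsules. If capsules are taken morning and night, the time-of-day shift could be close to zero. This stands: a reader might infer a large shift away from fixed times, but no clock times are given for either. What is certain is the change of cue to capsule intake.

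**The no-treatment arm's timing is not written.** That it stays on morning and night is a natural inference, not a statement. In either case it cannot follow the capsule cue.

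**A lift from taking a capsule may be placebo effect.** Section 1.2 defines the effect as improvement caused by receiving a sham treatment, so such a lift is not plainly an artefact. The narrower point remains: sampling pain only at that moment may overstate sustained relief, and the design cannot separate the two.

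**The percentages are illustrative.** Independence is doubtful for repeated ratings from one person. With no shift at all, a lag-1 correlation of 0.3 already raises the improvement rate under the permutation rule to about 7%, and 0.5 to about 12% to 13%. So 2.5% is only a nominal comparator.

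**Other outcomes offer a cross-check.** NRS and the pain questionnaires are collected at visits in every arm without the capsule cue. They help, but they do not replace the app ratings in the permutation rule.

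**The sentence on identical procedures is general rationale.** A no-treatment arm must lack some procedures. The timing of a pain rating need not be one of them.

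**Stronger readings that the documents do not support.** A reader might infer bias in active versus placebo, but both arms share the cue and a common shift cancels. A reader might infer bias in the gender comparison or in the prediction model's association with response. Men and women, and predicted responders and non-responders, follow the same instruction within an arm; a common shift changes base rates and adds label noise but does not by itself create an association. Nor should the point rest on how long after the previous dose the active arm is rated: with twice-daily capsules near morning and night, one common schedule could leave that interval much the same.

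**Conclusion.** The point holds for three contrasts: capsule arm versus no treatment, baseline-to-treatment change with the responder labels drawn from it, and treatment-to-washout change. In each, any treatment effect is mixed with a change in when pain is rated, and the written analysis has no means of separating them.

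The size and direction are unknown. The figures above are conditional on the assumed shift, SD, independence and rating counts. Under them, 0.3 to 0.5 points would matter a good deal for the permutation rule and moderately for the 20% rule, while about 0.1 points would matter little. Confidence is high in the inconsistency of the instructions and low in any particular amount of bias. It is worth removing because it touches the contrasts on which the trial's central claim rests and cannot be fully undone in analysis.

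**What to change.** In section 5.2.1 (Interim periods):

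- Delete the clause that ties treatment-period ratings to medication intake.
- State one morning-and-night rating schedule for all three arms and all periods, independent of capsule intake, and name the no-treatment arm explicitly.
- Have the app take the pain and mood rating before it shows the medication question.
- Bring the Visit 1 and Visit 3 instructions into line with that schedule.

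The cost is a short protocol edit and a change in app prompt order, with no extra visits or data. The drawback is that medication logging becomes less closely tied to the moment of intake; pill counts at Visits 4 and 5 remain as a separate adherence check. The change belongs before data collection, since later adjustment for rating time would address only the clock-time part.

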11. PUBLICATIONS -----27

12. REFERENCES -----28

13. SUPPLEMENTS/APPENDICES ----- 32

 I CONSENT FORM TEMPLATE ----- 32

 II LIST OF QUESTIONNAIRES ----- 40

 III AE COLLECTION FORM TEMPLATE ----- 41

 IV DSMP ----- 42

 V STUDY ROSTER -----111

 VI SCHEDULE OF EVALS & ASSESSMENTS ----- 114

 VII BIostatistician CV ----- 117

 VIII LABORATORY PROCEDURES & EVALUATIONS ----- 126

STUDY SCHEMA AND DESIGN

Design Schema for Objective 2 (Phase 2):

We intend to randomize 210 CBP patients into the study with the expectation that 140 will finish successfully. The entire duration of the study will be 12 weeks with an initial 3-week baseline period (visits 1-3), a 6-week treatment period (visits 3-5), and a final 3-week washout period (visits 5-6). During the baseline period eligible **participants will be predicted as placebo responders and non-responders** based upon baseline brain scan results and specific questionnaire answers (properties determined from the results of **Phase 1**) and then classified on that basis. Participants will then be randomized within each classification group (placebo responders and placebo non-responders) at a ratio of 3:3:1 such that 42.5% receive active medication (naproxen/omeprazole, 500/20mg, bid), 42.5% receive matching placebo treatment and 15% no treatment. Brain imaging, self-report questionnaire, and pain/mood rating measurement regimens are shown in **Figure 1**. Pain, mood, and pill ingestion will all be monitored by smart phone for the duration of the study, as well as determined in person at each visit.

[figure not shown]

Figure 1. Experimental schema for Phase 2. Expected changes in pain are shown in solid and dashed horizontal lines. We expect to see different pain outcomes for the various placebo and treatment combination groups. To be noted, we predict that the No Treatment group will have similar pain trajectory as those classified Non-responders and treated with placebo. As well, in the No Treatment group participants will be classified as placebo responders and placebo non-responders, but will not receive any treatment agent, therefore, their pain trajectory will be constant throughout the study.

STUDY SUMMARY

Title	BRAIN MECHANISMS FOR CLINICAL PLACEBO IN CHRONIC PAIN
Short Title	PLACEBO IN CHRONIC PAIN (PICP)
Protocol Number	Grant:
Phase	Grant Phase 2
Methodology	Double blind, randomized (see section 5.4 for more specifics on blinding)
Study Duration	12 weeks
Study Center(s)	Northwestern University

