- Visit 2 (week -1): Baseline Scan (90 min). Approximately 14 days after visit 1, participants will return for their second visit. If a VAS score of > 5 mm on average over the course of the visit 1-visit 2 rating period is calculated and no changes in clinical status are reported or found, they complete a battery of questionnaires and undergo MRI procedures (anatomical and functional scans). Subjects will be queried about changes to health experienced since the last visit and asked if they exceeded 4 acetaminophen per day. In addition one of the pictures for visit 2, 4, and 5 will be conducted (see section 13.III). They will be asked to continue their phone/computer app ratings and return in approximately one week for visit 3. Participants will receive only rescue medication in sufficient quantities until the next visit. Additionally, participants will be randomized into a treatment versus no-treatment group at this time (information that the pharmacy will produce and keep).
- Interim between Visit 2 and Visit 3: Group classification Based on Predicted Response

In between visits 2 and 3, participant's scans will be analyzed by extracting the functional connectivity between frontal and sensorimotor networks (called "sign permutation" in Equation 1) and 2 questionnaire subscores will be calculated (MAIA emotion and ERQ suppression in Equation 1); all 3 parameters will then be entered into Equation 1. Based on the results of the model specified on page 10, participants will be classified as either placebo non-responders (probability < 0.5) or placebo responders (probability \geq 0.5).

After baseline scan, the subjects' MR images and data will be collected by research personnel and then will be given to a single member, the blinded assessor ([name]) who will have no interaction with the participants, therefore will remain blinded. The research personnel responsible for conducting the visit will download the MAIA and ERQ questionnaires from the REDCap database and calculate the scores for MAIA-Emotion and ERQ-suppression subscales to be used in the model.

(1) All MR images collected at the baseline scan will be uploaded to the server and pre-processed within 24 hours of the visit using our in-house pipeline.

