whether or not they took their medication. This will allow us to keep track of the stability and magnitude of pain and mood, as well as treatment compliance. To encourage them to keep up with this requirement, each time they submit these answers, they will receive 25 cents. Responses and payments will be logged automatically into a secure database that only study personnel will have access to; if participants miss more than 3 consecutive ratings in a row, research personnel will call or text them to remind them to rate or verify that their app is still working (they are automatically alerted via email by a program designed by the lab). The unblinded monitor designated for this study will check participants ratings bi-weekly to verify that ratings are being completed.

- Follow up: Patients will be asked if they wish to be added to our contact list to participate in future studies of the lab. They will also be asked if they accept to be contacted by phone 3 months and 6 months later to assess the long-term effects of the study intervention on their chronic pain intensity.

5.3 Randomization:

All randomization (and blinding, see next section) will be completed by NUCATS (see study roster in Location 2 for name of personnel). NUCATS will generate two randomization sequences, one for each group (predicted responders, Group A, and non-responders, Group B). This approach will ensure the proper 3:3:1 treatment allocation. We will use a variable block design (size of 5 and size of 10), throughout Phase 2 of the study to minimize temporal bias that can accompany longitudinal scanning studies. We don't anticipate much exclusion after randomization and enrollment based on our previous studies (although screen failures during the run-in are likely due to pain level or pathology lab results, for example). The Phase 2 overall sample size is 210 randomized 3:3:1, therefore n = 90 active treatment (n = 45 responders/non-responders), n = 90 placebo treatment (n = 45 responders/non-responders), and n = 30 no treatment (n = 15 responders/non-responders). We expect an attrition rate of ~33% for a final N = 140.

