8.0 STATISTICAL CONSIDERATIONS

8.1 Summaries of Design, Endpoints, and Analysis

8.1.1 Phase II: Study Design/Study Endpoints

Enroll and randomize 220 CBP patients into the study. Stratify into placebo responders and non-responders based on brain scan results at entry. We anticipate that about 50% of the patients will be placebo responders. All participants are randomized so that 40 receive placebo treatment, 40 active medication, and 20 no treatment. If Gender Supplement is awarded then randomization is slightly different: 60 receive placebo, 60 active medication, and 20 no treatment.

We assume that placebo responders and non-responders will show differential interaction with active medication treatment. We also expect to distinguish the four groups based on brain activity at the end of the trial, and show close correspondence between predicted and actual outcomes regarding placebo responses. Additionally, placebo non-responders should show a robust medication response, especially in comparison to the placebo non-responders receiving placebo treatment. Brain activity contrasts are done as a two-way (treatment groups) repeated measures (time: start vs. end) ANOVA (2RM-ANOVA). This is the procedure we implemented recently in a longitudinal neuroimaging study of pain chronification (Baliki et al., 2012). Post-hoc comparisons then reveal: 1) A contrast of brain activity at end of treatment between placebo non-responders with and without medication treatment to identify brain activity for bottom-up modulation of chronic pain. 2) Brain regions related to chronic pain are identified as areas commonly decreased with placebo treatment for placebo responders and medication treatment for placebo non-responders. 3) Top-down placebo and bottom-up medication effects are distinguished by identifying regions that distinctly increase in activity for placebo and medication treatments based on contrasts for the same groups. 4) The no treatment group brain activity is used as a higher-level contrast, which effectively corrects for this confound.

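### Blocks of 5 and 10 do not fit the stated 3:3:1 allocation, and one Visit 2 sentence randomises before the strata are known

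*Combined protocol and SAP*

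**What the plan says.** **Ratio and blocks.** Section 5.3 has NUCATS produce two sequences, one for predicted responders (Group A) and one for predicted non-responders (Group B), and states: "This approach will ensure the proper 3:3:1 treatment allocation. We will use a variable block design (size of 5 and size of 10". It gives 210 randomised as 90 active, 90 placebo and 30 no treatment, or 45/45/15 in each stratum, with about 33% attrition leaving 140. The Study Schema agrees on the ratio: "Participants will then be randomized within each classification group (placebo responders and placebo non-responders) at a ratio of 3:3:1". So does step (4) of the interim between Visits 2 and 3 in 5.2.1: "Each group independently will be allocated in a 3:3:1 ratio (active treatment, placebo treatment, and no treatment, respectively) by the research pharmacy".

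**Section 8.1.1.** This section differs: "Enroll and randomize 220 CBP patients into the study", followed by "All participants are randomized so that 40 receive placebo treatment, 40 active medication, and 20 no treatment". It then gives 60/60/20 if the gender supplement is awarded.

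**Timing.** The Visit 2 text in 5.2.1 says "participants will be randomized into a treatment versus no-treatment group at this time". The scan analysis and classification come afterwards, between Visits 2 and 3. The appendix schedule of evaluations has the stratification result sent to the pharmacy so that randomisation can follow from it. The Visit 3 text says "Participants who remain eligible will then be randomized to active treatment, placebo, or no treatment groups in a blinded fashion", and also "The unblinded monitor will pick up study drug from the pharmacy prior to visit 3, if the participant is assigned to the treatment arm".

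**The concern.** A fixed-composition permuted block must be a multiple of the sum of the ratio. For 3:3:1 that is 7; for 2:2:1 it is 5. Two adjacent sentences of 5.3 therefore specify different things, and someone building the list in the usual way would not obtain the stated arm sizes. Under 5.4 the study staff, including the statistician, stay blinded until database lock, so those who analyse the trial could not see a wrong ratio until it was too late to correct.

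The Visit 2 sentence raises a separate problem. The Group A or Group B list cannot be used before the group is known. If the no-treatment arm were drawn at Visit 2, its stated 15/15 split between predicted responders and non-responders would no longer be ensured.

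**Working it through.** **Inputs.** Ratio 3:3:1, blocks of 5 and 10, N = 210 and final N = 140 (5.3); 40/40/20, 60/60/20 and about 50% responders (8.1.1); effect sizes d = 0.8 and d = 0.5 (8.1.2).

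**The plan's own figures.** 210 × (3, 3, 1)/7 = 90/90/30, and 105 × (3, 3, 1)/7 = 45/45/15. Both reproduce. 210 × (1 − 0.33) = 140.7, in line with 140. The ratio is 42.9/42.9/14.3%, which the Study Schema gives loosely as 42.5/42.5/15%.

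**Can the blocks hold the ratio?**

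| Block | At 3:3:1 | At 2:2:1 |
|---|---|---|
| 5 | 2.14/2.14/0.71 | 2/2/1 |
| 10 | 4.29/4.29/1.43 | 4/4/2 |
| 7 | 3/3/1 | not whole |
| 14 | 6/6/2 | not whole |

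Unequal blocks of 5 can average to 3:3:1. In a stratum of 105, 15 × (2,2,1) + 3 × (2,3,0) + 3 × (3,2,0) = 45/45/15. The documents give neither block contents nor an averaging rule.

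**Result with ordinary blocks of 5 and 10.** 210 × (2, 2, 1)/5 = 84/84/42. Two thirds completing gives 56/56/28, against 60/60/20 at 3:3:1.

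**Power** (two-sample t test, two-sided alpha 0.05, completers):

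| Comparison | Ratio | n | d = 0.5 | d = 0.8 |
|---|---|---|---|---|
| Active v placebo, all | 3:3:1 | 60 v 60 | 77.5% | 99% |
| Active v placebo, all | 2:2:1 | 56 v 56 | 74.6% | 99% |
| Active v placebo, one stratum | 3:3:1 | 30 v 30 | 47.8% | 86.1% |
| Active v placebo, one stratum | 2:2:1 | 28 v 28 | 45.1% | 83.6% |
| Placebo v no treatment | 3:3:1 | 60 v 20 | 48.1% | 86.4% |
| Placebo v no treatment | 2:2:1 | 56 v 28 | 57.0% | 92.7% |

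Active against placebo loses under 3 points; placebo against no treatment gains 6 to 9.

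**Where the sizes may come from (inference).** 40/40/20 in 8.1.1 is 2:2:1, which blocks of 5 and 10 fit. Section 8.1.2 says the gender supplement raises each treatment group by 50% (40 × 1.5 = 60), and the sample-size section of the DSMP says it adds 40 patients (100 + 40 = 140). The result, 60/60/20, is 3:3:1 and equals the 140 completers. The block sizes may have been left behind when the ratio changed.

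**Timing.** The Study Schema, step (4), 5.3 and the appendix schedule all classify first and then allocate within stratum; the Visit 2 sentence alone does the reverse. If 30 no-treatment patients were drawn without stratification from 105:105, the hypergeometric probability of a 10:20 or more uneven split is 0.075.

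The Visit 3 wording is a lesser matter. Randomisation is described as a Visit 3 step there and in the appendix, yet drug is collected by arm before that visit, and the appendix calls the medication already randomised. This reads as loose wording for the same post-classification assignment.

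**The case against.** The intended ratio is not in doubt: three places say 3:3:1, and 5.3 gives explicit counts. NUCATS would have to override all of that to build 2:2:1, so the defect may be no more than a stale parenthesis, and a list of unequal blocks could meet 45/45/15 exactly. The Visit 2 sentence likewise stands alone against several passages that put classification first. The 7.5% figure needs that sentence to be followed, exactly 30 to be drawn unstratified, and an exact 105:105 split. No planned analysis splits the no-treatment arm by stratum, and stratum can be a covariate. Finally, fixing assignment before drug pick-up puts it ahead of the Visit 3 eligibility check, which could create exclusions after randomisation.

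Most of this stands as a limit on the harm. It does not remove the inconsistency: the protocol should allow the randomisation to be reproduced, and as written it does not. The eligibility point is fair, and the fix has to deal with it.

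**Conclusion.** The concern holds. Section 5.3 is wrong as written, because its block sizes cannot deliver its own ratio without a scheme that the plan does not describe. The Visit 2 sentence contradicts stratified allocation. That is certain from the text. The 84/84/42 outcome is conditional on ordinary fixed-composition blocks having been used, and the documents cannot show whether they were.

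If they were, the no-treatment arm is 40% larger than stated (42 against 30) and each pill arm is 6 smaller. The totals of 210 and 140 do not change. The power figures assume equal attrition across arms, and those for one stratum also assume a 50:50 split. This should be fixed, but it does not threaten the main comparisons.

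**What to change.** **Section 5.3.** Replace the block sizes with multiples of 7 (for example 7 and 14) in each stratum list, and have NUCATS confirm the ratio of any list already built. Note that 45/45/15 per stratum holds only at a 105:105 split (at 84:126 it is 36/36/12 and 54/54/18), and that 4.4 allows further enrolment.

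**Only if a 2:2:1 list is in use.** Regenerate it for participants not yet randomised. After m participants the expected arms are 90 − m/35, 90 − m/35 and 30 + 2m/35: 88/88/34 at m = 70, 87/87/36 at m = 105, 86/86/38 at m = 140. Restate the arm sizes and adjust the analysis for list period, since the ratio would then differ by enrolment period.

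**Section 5.2.1 and the appendix schedule.** Delete the Visit 2 sentence. State one assignment, from the stratum list, after classification and before drug pick-up. Reword Visit 3 so that it dispenses that assignment, and say how a person assigned but found ineligible at Visit 3 is counted.

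**Section 8.1.1.** Replace 220 with 210, state whether the gender supplement applies, and keep only the allocation that follows (about 60/60/20 completers under the 3:3:1 design).

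**Cost.** Wording only if the lists already average 3:3:1. Otherwise: new lists for future participants, arm sizes that will not be exactly 90/90/30, and one extra covariate. No extra patients or procedures.
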